#### 10.2.14 Pharmacokinetics

PK samples will be collected for tideglusib and the major metabolite NP04113 at both [REDACTED]  
[REDACTED]  
[REDACTED]  
[REDACTED]  
[REDACTED].  
[REDACTED]  
[REDACTED]  
[REDACTED]

Individual concentration data will be determined and  $T_{max}$ ,  $T_{1/2}$ ,  $AUC_{(0-12hr)}$ ,  $C_{max}$ ,  $C_{min}$  and  $C_{ss}$  will be calculated. Population pharmacokinetic methods of analysis will be used to analyze the data. If the data does not support a model on its own, the data may be combined with a previously developed model in order to strengthen the predictions.

In order to determine whether there are associations between pharmacokinetic parameters and efficacy measures, change from baseline in efficacy measures over the course of the study may be correlated with PK parameters estimated for each dose. These associations may be statistically tested using correlation coefficients and general linear models, if appropriate.

Instructions for the collection, handling, storage, processing and shipment of the pharmacokinetic samples will be provided in a separate laboratory manual.

### 10.3 Other Assessments

#### 10.3.1 Diary

A diary will be provided to the subject/caregiver at each visit from Run-in [REDACTED] to Week [REDACTED] which should be completed every day. The diary should be returned at each subsequent visit and the diary should be reviewed by a delegated member of the study team.

The diary should be completed in full so that the following can be ascertained:

- Time and date of each dose
- If there was any issue with taking the dose
- Whether the subject [REDACTED]
- Time of [REDACTED]
- Type of food [REDACTED]

If any information is missing, this should be discussed with the caregiver so that missing information can be completed from the caregiver's recollection. It must be documented in the medical notes which information has been completed retrospectively.

The diary review should be performed in parallel with checking returned used and unused sachets of IMP.

### 10.3.2 [REDACTED]

For purposes of inclusion in the study, subjects need to have a confirmed genetic diagnosis of myotonic dystrophy type 1 [REDACTED]  
[REDACTED]  
[REDACTED]  
[REDACTED]

Where possible and with additional consent, [REDACTED]  
[REDACTED]

Instructions for the collection, handling, storage, processing and shipment of the [REDACTED] will be provided in a separate laboratory manual.

### 10.3.3 [REDACTED]

A 5ml blood sample will be taken for [REDACTED] analysis at the timepoints described in the schedule of assessments.

Instructions for the collection, handling, storage, processing and shipment [REDACTED] will be provided in a separate laboratory manual.

## 10.4 Adverse events

Adverse events may be volunteered spontaneously by the subject, or discovered as a result of general, non-leading questioning. All adverse events should be recorded in the CRF and source document.

#### **10.4.1 Definitions**

##### Adverse Event (AE)

Any untoward medical occurrence in a patient or clinical trial subject administered a medicinal product and which does not necessarily have a causal relationship with this treatment. An adverse event (AE) can therefore be any unfavourable and unintended sign (including an abnormal laboratory finding, for example), symptom, or disease temporally associated with the use of a medicinal product, whether or not considered related to the medicinal product.

Abnormal laboratory findings should be reviewed by a delegated physician to determine whether they are clinically significant. Clinically significant abnormal laboratories should be reported as an AE. Where possible and underlying diagnosis should be reported as the AE.

##### Adverse Drug Reaction (ADR)

All events considered to be untoward and unintended responses to a medicinal product related to any dose should be considered adverse drug reactions. The definition covers also medication errors and uses outside what is foreseen in the protocol, including misuse and abuse of the product. The phrase “responses to a medicinal product” means that a causal relationship between a medicinal product and an adverse event is at least a reasonable possibility, i.e., the relationship cannot be ruled out.

##### Serious Adverse Event (SAE)

An adverse event that at any dose:

- Results in death
- Is life-threatening (i.e. the subject was at risk of death at the time of the event; it does not refer to an event which hypothetically might have caused death if it was more severe)
- Requires inpatient hospitalisation or prolongation of existing hospitalisation (see explanation below)
- Results in persistent or significant disability/incapacity
- Is a congenital anomaly/birth defect
- Is considered to be an important medical event

Based upon medical and scientific judgment, important medical events that may not be immediately life-threatening, or result in death or hospitalisation, but may jeopardise the subject or may require intervention to prevent one of the other outcomes listed in the definition above may be considered a serious adverse event.

Hospitalisations are defined as initial or prolonged admissions that include an overnight stay. Hospitalisation or prolonged hospitalisation for technical, practical or social reasons, in the absence of an adverse event is not an SAE.

### Pregnancy

Pregnancy itself is not considered an AE. However, any pregnancy complication, spontaneous or elective abortion (for medical reasons), still birth, neonatal death, or congenital anomaly will be recorded in both the clinical and safety database.

If the investigator becomes aware of a pregnancy in a female subject, or in a female partner of a male subject in this study, every effort will be made to follow the pregnancy until termination or delivery.

In the event of pregnancy (either in a female subject or a female partner of a male subject in the study), it will be reported on a pregnancy form, and reported as per the information in section 10.4.8. This report will be followed up to determine outcome, including spontaneous or voluntary termination, details of birth, and the presence or absence of any birth defects or congenital abnormalities. The outcome will be documented in the CRF if feasible. In the case of a female subject, the subject must be withdrawn from the study.

Due to the disease under study and the potential intellectual disability of the study subjects, along with the age of some of the potential study subjects, information on how and to whom, a positive pregnancy result will be communicated will be addressed in the study information sheet.

### Unexpected Adverse Drug Reaction

An adverse reaction, the nature or severity of which is not consistent with applicable product information (e.g., Investigators Brochure for an unapproved Investigational Medicinal Product).

#### Suspected Unexpected Serious Adverse Reaction (SUSAR)

A serious AE that is suspected to be related to the administered medicinal product and the nature or severity of which is not consistent with applicable product information.

Reports which add significant information on the specificity, increase of occurrence, or severity of a known, already documented serious adverse reaction constitute unexpected events.

### **10.4.2 Severity Categorisation**

The severity (intensity) of each AE will be classified as:

- **Mild** Awareness of sign or symptom, but easily tolerated

- **Moderate** Sign or symptom causes discomfort, but does not interfere with normal activities
- **Severe** Sign or symptom of sufficient intensity to interfere with normal activities

A change in severity should be captured as a new AE.

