#### **STUDY ENDPOINTS**

Primary endpoint:

- Incidence of adverse events (AE), including Serious adverse events (SAE). AEs will be evaluated between baseline and Follow-up Visit, while SAEs will be evaluated between screening and the last clinic visit or until resolution, whenever possible. The incidence of abnormal findings in objective assessments (e.g. laboratory values, ECGs, and vital signs) during the course of the study will also be assessed.

Secondary endpoints:

- Blood pharmacokinetics (PK) of tideglusib
- 10 metre walk/run test (self-selected and fastest velocity)
- Computerised handgrip myometer measure of grip strength and muscle relaxation time
- Respiratory Forced Vital Capacity (FVC)
- Dual-energy X-ray absorptiometry (DXA) whole body scan of lean muscle mass (g) legs, arms, and total
- Clinical Global Impressions– Severity and – Improvement (CGI-S and CGI-I)
- Actigraphy (measure daily averages of: number of bouts of activity, number of steps taken and energy expenditure)
- Nine Hole Peg Test (NHPT)
- Top 3 Concerns Visual Analogue Scale (VAS) (caregiver-completed and where possible, also subject-completed)
- OSU Autism Rating Scale (OARS)
- OSU Autism CGI
- Clinician-completed Domain Specific Causes for Concern VAS: Myotonic Dystrophy
- Peabody Picture Vocabulary Test (PPVT)
- [REDACTED] levels and activity

PLANNED SAMPLE SIZE AND  
STATISTICAL  
CONSIDERATIONS

16 Subjects are planned to be enrolled.

Adverse event and other safety data will be summarised as frequencies and percentages, and described in terms of severity and relationship to study treatment. Objective safety assessments, including laboratory and ECG values, will be summarised by treatment period (screening, run-in, [REDACTED] treatment) and treatment dose. Changes in safety parameters over time will be described, and shift tables at time points of interest will be generated as required.

Analyses of changes in efficacy variables from baseline will be performed where applicable using repeated measures

analysis of covariance (ANCOVA) models with study site (if more than one is used) and treatment dose as fixed effects, and baseline value as a covariate. Least square mean estimates will be produced by dose group and study visit and will be presented with 95% confidence intervals and two-sided p-values.

The safety and efficacy analyses will be specified in detail in the Statistical Analysis Plan (SAP).

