#### **10.4.6 Clinical Laboratory Evaluations**

Abnormal laboratory findings (e.g. haematology, liver function, biochemistry, urinalysis) or other abnormal assessments (e.g. ECGs, vital signs) that are judged by the Investigator as clinically significant will be recorded as AEs or SAEs if they meet the definition of an AE, as defined in Section 10.4.1

Clinically significant abnormal laboratory findings or other abnormal assessments that are detected during the study and significantly worsen following the start of the study will be reported as AEs or SAEs.

The Investigator will exercise his or her medical and scientific judgment in deciding whether an abnormal laboratory finding or other abnormal assessment is clinically significant.

Subjects with any TEAE laboratory abnormality (especially LFT abnormalities) will be followed up until recovery or stabilisation of the condition.

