7 SAFETY EVALUATION

7.1 Adverse Events

Adverse events will be coded using the latest MedDRA dictionary version.

A NTEAE is defined as an AE that started on or after the administration of placebo treatment but before the start of the administration of active treatment.

A TEAE is defined as an AE that started on or after the start of the administration of active treatment. If adverse event dates are incomplete and it is not clear whether the adverse event was treatment-emergent, it will be assumed to be treatment-emergent.

A "treatment period" TEAE is defined as an AE that started on or after the start of active treatment but before 2 days after active treatment was discontinued. A "post treatment period" TEAE is defined as an adverse event that started from 2 days after the active treatment was discontinued.

Adverse events of special interest (AESIs) are recorded if it is identified from a review of the haematology and biochemistry results that the subject has clinically significant liver function test elevation.

The following summaries of the total number of “treatment period” TEAEs, “post treatment period” TEAEs and all TEAEs (both “treatment period” and “post treatment period” TEAEs) will be provided at the event and subject levels as indicated:

- TEAEs (events and subjects).
- TEAEs by relationship to active treatment (events and subjects).
- TEAEs by severity (mild/moderate/severe) (events and subjects).
- Serious TEAEs (events and subjects).
- Serious active treatment related TEAEs (events and subjects).
- TEAEs leading to withdrawal (subjects only).
- TEAEs leading to discontinuation of active treatment (subjects only).
- Active treatment related TEAEs leading to discontinuation of active treatment (subjects only).
- TEAEs leading to death (subjects only).

The following summaries of NTEAEs will be provided at the event and subject levels as indicated:

- NTEAEs (events and subjects).
- NTEAEs by severity (mild/moderate/severe) (events and subjects).
- Serious NTEAEs (events and subjects).
- NTEAEs leading to withdrawal (subjects only).
- NTEAEs leading to death (subjects only).

In the above summaries, if a subject experienced more than one NTEAE/TEAE, the subject will be counted once using the most related event for the “by relationship to active treatment” summary and at the worst severity for the “by severity” summary.

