The number and percentage of subjects experiencing “treatment period” TEAEs, “post treatment period” TEAEs and all TEAEs will be presented by:

1. System Organ Class (SOC) and Preferred Term (PT).
2. PT.
3. SOC, PT and severity.
4. SOC, PT and relationship (related/unrelated) to active treatment.

In addition, the number and percentage of subjects experiencing NTEAEs will be presented by:

1. SOC and PT.
2. SOC, PT and severity.

For all the above, SOC and PT will be presented in decreasing frequency of the total number of subjects with NTEAEs/TEAEs.

Further details of the above four tables are given below:

1. If a subject experienced more than one NTEAE/TEAE, the subject will be counted once for each SOC and once for each PT.

2. If a subject experienced more than one TEAE, the subject will be counted once for each PT.
3. If a subject experienced more than one NTAE/TEAE, the subject will be counted once for each SOC and once for each PT at the worst severity.
4. If a subject experienced more than one TEAE, the subject will be counted once for each SOC and once for each PT using the most related event.

Adverse event data will be listed in full and this will also include a treatment emergent flag, a treatment period TEAE flag, a post treatment period TEAE flag, a flag for AESIs, the time of onset of event relative to first dosing of active treatment, and duration of AE.

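### The AE severity scale cannot rank symptom-free liver test rises, and the SAP's AESI flag and low/normal/high shift tables do not make up for it

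*Protocol*

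**What the plan says.** **Severity scale.** Protocol 10.4.2 applies to all events: "The severity (intensity) of each AE will be classified as" mild, moderate or severe. The top grade is defined as "Sign or symptom of sufficient intensity to interfere with normal activities". The middle grade needs discomfort that leaves the subject's usual activities unaffected. The bottom grade is "Awareness of sign or symptom, but easily tolerated".

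Moving from one grade to another opens a new AE record. No laboratory criterion is given.

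**What counts as an AE.** Protocol 10.4.1 counts an abnormal laboratory finding as a sign that can be an AE. Under 10.4.6, abnormal laboratory and other assessments "that are judged by the Investigator as clinically significant will be recorded as AEs or SAEs". Neither section requires a symptom. Section 10.4.6 stresses follow-up of liver abnormalities in particular.

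**Use of the grade.** The Protocol Synopsis says AE data will be "described in terms of severity and relationship to study treatment". SAP 7.1 uses the three grades in its overview of TEAEs and in a table by SOC, PT and severity, where "the subject will be counted once for each SOC and once for each PT at the worst severity".

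**Liver tests in the SAP.** SAP 7.1 defines one event of special interest: "Adverse events of special interest (AESIs) are recorded if it is identified from a review of the haematology and biochemistry results" that a subject has a clinically significant liver test rise. It appears as a flag in the AE listing. SAP 7.2 summarises observed values and changes, classes each parameter as low, normal or high for shift tables, and lists all values and the out-of-range values.

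**The concern.** The scale measures how an event feels and what it stops the subject doing. A raised ALT usually has to be judged on its value. If the grade takes no account of the value, the severity tables cannot separate a trivial liver finding from an important one, or compare the two doses on that point.

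This matters because liver test elevation is the only harm the SAP singles out by name, and safety is the primary objective. It would matter less if another SAP table sorted liver rises by size, so the check has to cover those outputs too.

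**Working it through.** There is no figure in the plan to reproduce. The check applies the definitions and then traces the outputs.

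**Step 1: apply Protocol 10.4.2 to a symptom-free ALT rise of k times ULN.**

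| Grade | Requires | Met by a rise the subject does not feel? |
|---|---|---|
| Severe | interference with normal activities | No, for any k |
| Moderate | discomfort | No, for any k |
| Mild | awareness, easily tolerated | Fits poorly, but is the only grade left |

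Every AE must have a grade, so *mild* follows by elimination. Because even *mild* speaks of awareness, an investigator may instead improvise, and equal values may get different grades. If the rise grows without symptoms, the grade on this scale does not change and the new-record rule is not triggered.

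**Step 2: trace where the size of a silent liver rise could appear in the SAP.**

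| Output | Shows its size? |
|---|---|
| 7.1 TEAEs by severity; by SOC, PT and severity | No (Step 1) |
| 7.1 serious TEAEs | Only that it was judged serious |
| 7.1 TEAEs leading to withdrawal or discontinuation | Only that treatment or participation ended |
| 7.1 AESI | Listing flag; no count specified |
| 7.2 summary statistics (with maximum, per SAP 1) | Largest value in the group at a visit, but not how many subjects or from what baseline |
| 7.2 shift tables | No (Step 3) |
| 7.2 listings | Yes, subject by subject |
| 7.3 and 7.4 size bands | Blood pressure, heart rate and QT/QTc only |

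**Step 3: shift tables.** All values above ULN are one category, so a normal-to-high shift looks the same just above ULN and far above it. Exclusion criterion 14 in Protocol 7.3 excludes ALT above 2 times ULN. A subject between 1 and 2 times ULN can therefore enter (criterion 13 permitting) and have a high baseline. That subject stays high-to-high however far ALT rises.

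**Step 4: size.** Protocol 11.1 plans 8 subjects per dose, and SAP 1 bases AE percentages on the analysis set.
- One subject is 1/8 = 12.5 percentage points of a dose group's row, or 1/16 = 6.25 points over both groups.
- Severe in 0/8 is 0%; exact 95% upper limit 1 − 0.025^(1/8) = 36.9%.
- Severe in 1/8 is 12.5%; exact 95% interval 0.3% to 52.7%.

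The second and third lines are only an illustration. They assume that a value-based scale would put one such event in the top grade.

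**The case against.** The other side has a good deal of substance.

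- **Severity is not the primary endpoint.** Protocol 8.1 names AE incidence and, separately, how often objective assessments are abnormal. Severity is a descriptive breakdown. This stands.
- **ECG and vital signs are covered.** SAP 7.4 counts QT, QTcF and QTcB above 450, 480 and 500 msec and changes beyond 30 and 60 msec. SAP 7.3 counts large blood pressure and heart rate changes. This stands, and the point is therefore limited to liver tests.
- **Important events show elsewhere.** A reader might infer that a table with no severe events would hide subjects who stopped treatment for liver values. The documents do not support that: SAP 7.1 has serious, withdrawal and discontinuation rows, SAP 4.1 summarises reasons for withdrawal, and SAP 4.4 lists down-titration.
- **The protocol never says a silent finding is mild.** Correct; that is an inference by elimination. The alternative is grading with no guidance, which is also a defect.
- **Some text is not visible.** The individual stopping criteria and laboratory alert values in Protocol 9.6 are redacted. It cannot be said that a value meeting one of them would be graded mild, since such a criterion might also require symptoms. The table shells are a separate document, so a liver display may exist there.
- **Overwriting investigators' grades would be a mistake.** SAP 3.1 shows that Cohort 1 outputs have been reviewed, and Appendix 1 includes all biochemistry values among them. Limits devised now would be open to the charge of being data-driven. This stands and shapes the fix.

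The liver gap remains. The QT bands show that the SAP accepts size categories for a laboratory-type finding, yet its readable text has none for liver tests.

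**Conclusion.** The point holds for liver tests. Protocol 10.4.2 cannot rank a symptom-free liver AE, and neither the AESI flag nor the SAP 7.2 shift tables supply the missing ranking. The understatement is limited to the severity tables and the liver shift tables. It does not reach AE incidence, serious events, discontinuations, ECG or vital signs, and the listings still hold every value.

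Each affected subject is worth 12.5 percentage points of a row in a group of 8. How many there will be is unknown: the documents give no expected rate, and whether any event is understated depends on the data. The conclusion rests on the readable text, and on the table shells and CRF guidance adding no value-based liver grade. The change should be made, but the primary endpoint can be reported without it.

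**What to change.** **Protocol 10.4.2.** State that the present definitions apply to symptomatic events, and that laboratory AEs are graded on the measured value using an established published scale, named before final database lock.

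**SAP 7.1 and 7.2.**
- Derive that grade by program from the stored laboratory values for both cohorts.
- Show it beside the investigator's recorded severity, without overwriting it.
- Tabulate by dose the maximum post-baseline liver tests in multiples of ULN, with baseline category.
- Tabulate by dose the number of subjects with an AESI.

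**Cost.** A short protocol and SAP text change and some programming; no new data are needed. Liver counts may look less favourable. The report must say that the limits were set after Cohort 1 outputs had been reviewed; taking them unaltered from a published scale limits that weakness. The change concerns classification and reporting only, and no stopping or dosing rule is altered.

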#### **10.1.5 Adverse Event Collection**

Subjects will be questioned in a non-leading way to determine if AEs have occurred since the last visit e.g. have you had any health problems since your last visit?" SAEs will be collected from the time of informed consent. Non-serious AEs will be collected from the time of single-blind dosing. Any non-serious medical occurrences occurring between Screening █ and Run in █ will be recorded as Medical/Surgical History. Any non-serious signs and symptoms occurring between Screening █ and Run in █ will be recorded and classified as baseline signs and symptoms. Refer to section 10.4 for additional details of AE collection and reporting.

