#### **10.4.3 Assessment of Causality**

A delegate physician/investigator must assess the relationship to the IMP for each AE. The likely relationship of each AE to the IMP will be assessed according to the definitions below:

- Unrelated
- Related

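### Read literally, the AE rules class an event that began in the placebo run-in and only eased on tideglusib as treatment-emergent

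*Protocol*

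**What the plan says.** **Recording.** Protocol 10.4.2 defines mild, moderate and severe, then adds: "A change in severity should be captured as a new AE". The rule is not limited to increases. Protocol 10.1.5 says "Non-serious AEs will be collected from the time of single-blind dosing", so an AE can start in the placebo run-in and still be present when tideglusib begins. Under Protocol 10.4.3, "A delegate physician/investigator must assess the relationship to the IMP for each AE", so each new record also receives its own causality rating.

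**Classification.** SAP 7.1 uses start dates only. A non-treatment-emergent AE (NTEAE) is one that "started on or after the administration of placebo treatment but before the start of the administration of active treatment". For active treatment, "A TEAE is defined as an AE that started on or after the start of the administration of active treatment". For the later window, a post-treatment-period "TEAE is defined as an adverse event that started from 2 days after the active treatment was discontinued". Nothing in the section asks whether the event worsened, and nothing joins records belonging to one episode.

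**Tabulation.** SAP 7.1 gives TEAE totals as events and as subjects, for the treatment period, for the post-treatment period and for both together. In the table by SOC, PT and severity, "the subject will be counted once for each SOC and once for each PT at the worst severity". The other SOC and PT tables also count a subject once.

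**The concern.** Each rule is workable alone. Together they make improvement look like a new event. If a run-in AE drops from severe to moderate in the first days of tideglusib, nothing new or worse has happened on drug, yet a record with an on-drug start date now exists and meets the TEAE definition. The same subject then appears in both the NTEAE table and the TEAE table for one episode.

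This matters because AE incidence is the primary endpoint (Protocol 8.1) and there is no concurrent placebo group. The run-in NTEAE tables are the only on-placebo AE data to set beside the TEAE tables, so the boundary between them should be clean. Both tables by SOC and PT are also among the Cohort 1 outputs (SAP 3 and Appendix 1).

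The wording is also out of step with the rest of the Protocol. Under 10.4.9 a baseline sign or symptom becomes an AE only on worsening, and under 10.1.2 improvement of a finding from the medical history goes to the source document.

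**Working it through.** The plan states no figure on this point, so there is nothing to reproduce. The check applies the written rules to hypothetical episodes and compares them with an episode-level rule: one episode counted once, and a TEAE only if onset or worsening falls on or after first active dosing.

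**Inputs**
- New record at any severity change: Protocol 10.4.2.
- Class by start date: SAP 7.1.
- n = 8 per dose group: Protocol 11.1 and SAP 2.4.
- Assumption: the new record's start date is the date of the severity change. The documents do not say this, but it is the natural reading of a new AE.

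Day 0 is the first tideglusib dose.

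**Case 1: starts on placebo, eases on drug.** Severe on day −5, moderate on day +3, mild on day +8.
- As written: the day −5 record is an NTEAE, and the day +3 and day +8 records are TEAEs. Result: 1 NTEAE, 2 TEAE events, 1 TEAE subject. The worst-severity rule works within each table, so the TEAE table shows moderate.
- By episode: 1 NTEAE, 0 TEAEs.
- Incidence for that PT, with no other on-drug record of it in the group: 1/8 = 12.5% (exact 95% CI 0.3 to 52.7) as written, against 0/8 = 0% (0 to 36.9) by episode. Difference: 12.5 percentage points.

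**Case 2: on-treatment AE eases after stopping.** Moderate during treatment, mild from 3 days after the last dose.
- As written: one treatment-period TEAE and one post-treatment-period TEAE. By episode: one treatment-period TEAE.
- The table of all TEAEs counts the subject once for the PT either way. Only the split between periods, and the event total (2 against 1), change.

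**Case 3: fluctuation wholly on treatment.** Mild, moderate, severe, moderate, mild.
- An episode with k severity changes gives k + 1 records. Here k = 4, so there are 4 + 1 = 5 TEAE events against 1 by episode.
- Subject count: 1 either way.

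**Case 4: starts on placebo, worsens on drug.** Mild in the run-in, moderate after day 0.
- As written: the moderate record is a TEAE. By episode: also a TEAE, with onset at the date of worsening. The recording rule does useful work here and should be kept.

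| Case | TEAE events, as written / by episode | TEAE subjects, as written / by episode |
|---|---|---|
| 1 | 2 / 0 | 1 / 0 |
| 2 | 2 / 1 | 1 / 1 (period split changes) |
| 3 | 5 / 1 | 1 / 1 |
| 4 | 1 / 1 | 1 / 1 |

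Only case 1 changes subject-level TEAE incidence.

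**The case against.** **Sites may read the rule as worsening only.** Protocol 10.4.1 defines an AE as something unfavourable, the neighbouring rules in 10.4.5, 10.4.6 and 10.4.9 turn on worsening, and 10.4.4 offers an outcome category for an event that is resolving. A site could reasonably leave an easing event on its existing record. That lowers confidence that easing would always be entered as a new AE. It does not settle the matter, because 10.4.2 itself contains no such limit and the outcome field does not exempt easing events from it.

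**The reach is narrow.** A reader might infer that all three patterns inflate the primary endpoint. The documents do not support that. Counting a subject once per SOC and PT confines case 3 to the event totals, and the all-TEAE tables absorb case 2. Case 1 needs several things together: a run-in AE that lasts past the first active dose, steps down rather than resolves, is entered as new, and is the subject's only on-drug record of that PT. For overall any-TEAE incidence, the subject must have no other TEAE at all. This objection stands and sets the size of the point.

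**The data are visible and the error is cautious.** Every AE is listed with its flags, onset relative to first active dosing and duration. The DSMC sees all AE data, no test is planned on AEs, and any error over-counts harm. All true, but a listing does not correct a summary table, and its onset and duration columns would describe fragments of an episode.

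**Linking brings its own risk.** Joining records by date can merge distinct events, and the sponsor who would review links knows the treatment (Protocol 9.3). This stands, and it is why the linking rule must be written in advance.

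**Conclusion.** The concern holds in a limited form. As worded, the two rules put an easing run-in AE in the TEAE table. That is a wrong class produced by a stated rule, not a missing detail. The effect on a PT is 12.5 percentage points for each affected subject in a group of 8, provided that subject has no other on-drug record of the PT. Easing 2 or more days after stopping distorts only the post-treatment split, and multiple severity changes distort only event totals.

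Two limits apply. The result rests on the new record starting on the date of the severity change, and the frequency of step-downs cannot be known from the documents. It would therefore be wrong to conclude that TEAE incidence in this trial is materially overstated. The supportable statement is that the definition permits it and the SAP contains nothing to prevent it.

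**What to change.** Amend SAP 7.1 and leave the CRF rule in Protocol 10.4.2 as it is, so that worsening is still captured.

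1. **Link.** Pre-specify that records of the same PT in one subject form one episode when the stop date of one equals the start date of the next. Settle ambiguous links, such as a missing stop date, by a written rule fixed before database lock. This limits discretion by a sponsor who knows the treatment.
2. **Count.** Count each episode once in event tables, at its maximum severity within the period.
3. **Classify.** Class a record that continues an earlier one as a TEAE only if the episode first started, or its severity increased, on or after first active dosing. Class it as post-treatment-period only if it first started, or its severity increased, from 2 days after the last active dose.
4. **Date.** For an episode that worsens, use the date of worsening as the TEAE onset.

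**Cost.** A few lines of SAP text, a linking step in the AE dataset and review of a small number of links. No new data are needed. SAP 3.1 shows that the planned Cohort 1 outputs have already been produced and reviewed, so the Cohort 1 TEAE and NTEAE tables should be re-run under the same definition.
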